**Clinical Study Protocol**  
**Johnson & Johnson Vision Care, Inc.**

Visit 1: Baseline			
Step	Procedure	Details	
1.8	CLUE Baseline Questionnaire	The subject will respond to the PRO Baseline CLUE Questionnaire	Appendix A
1.9	Entrance Visual Acuity	Record the distance Snellen visual acuity (OD, OS, and OU) to the nearest letter with their habitual contact lens correction in place. Subjects must read the smallest line until at least 50% of the letters are read incorrectly.	
1.10	Remove Habitual Contact Lenses	The subject's habitual lenses will be removed and stored in their own lens case. If they forgot to bring their lens case, one will be provided to them.	
1.11	Iris Color	Record iris color in both eyes (self-reported)	
1.12	Horizontal visible iris diameter (HVID)	Measure the horizontal visible iris diameter for each eye separately using a pd stick in normal room illumination. Measure from the edge of the iris nasally to the edge of the iris temporally. Record in mm to one decimal place.	
1.13	Keratometry	Record the keratometry readings OD and OS.	
1.14	Subjective Spherocylindrical Refraction	Complete subjective spherocylindrical refraction and record the resultant distance visual acuity (OD, OS and OU) to the nearest letter. Note: The subjects contact lens powers based on the vertexed (12 mm), spherical equivalent must be between -1.00 and -6.00 D.	
1.15	Slit Lamp Findings	FDA Slit Lamp Classification Scale will be used to grade the findings and determine eligibility.  If any slit lamp findings are Grade 3 or higher, the subject is ineligible to continue. Continue to the Final Evaluation Form and dismiss the subject.  If the clearance of the fluorescein needs to be expedited, preservative-free rewetting drops or saline may be instilled.	
1.16	Eligibility after Baseline	All responses to Inclusion Criteria questions must be answered "yes" and all responses to Exclusion Criteria questions must be	

# Clinical Study Protocol

## Johnson & Johnson Vision Care, Inc.

	answered “no” for the subject to be considered eligible.	
--	--	--

Visit 1: Treatment 1 Lens Fitting			
Step	Procedure	Details	
1.17	Lens Selection	Assign the study lens based on the randomization scheme. Select the contact lens power based on the vertexed (12 mm), spherical equivalent subjective refraction.	
1.18	Lens Insertion	The Subject inserts the study lenses. Record the time of lens insertion. Check for lens damage under the slit lamp before proceeding with lens settling. Replace damaged lenses if applicable. Note: Designated site staff should observe the insertion process. If it appears that the subject attempts to insert a lens that is “inside-out”, they should interfere to avoid incorrect insertion.  Note 2: If the lens moves excessively on the eye after insertion, ask the subject to remove the lens, confirm lens is not inverted (correct if it is) and reinsert.	
1.19	Lens Settling	Allow the study lenses to settle for a minimum of 5 minutes.	
1.20	Subjective Best Sphere Over Refraction	Perform subjective best sphere refraction over the study lenses with a phoropter (adopt the maximum plus to maximum visual acuity (MPMVA) approach and use the duo-chrome test for binocular balancing) and record the best corrected distance visual acuity to the nearest letter (OD, OS, OU).	
1.21	Lens Power Modification (if applicable)	Adjust the lens power if the subject’s best sphere over-refraction is not plano. For each power modification, repeat steps (1.16 to 1.19). Two power modifications are allowed.	
1.22	Visual Acuity	Record the distance Snellen visual acuity (OD, OS, and OU) to the nearest letter with the study contact lens correction in place. Subjects must read the smallest line until at least 50% of the letters are read incorrectly.	

**Clinical Study Protocol**  
**Johnson & Johnson Vision Care, Inc.**

1.23	Distance ETDRS LogMAR Visual Acuity	
Per [REDACTED], please confirm room illuminance and chart luminance acceptable ranges for both high/low contrast visual acuity testing.
 
 
1. Under high illumination and high chart luminance, record the distance (4 meter) ETDRS high contrast visual acuity twice OD (HC1-HC2) and twice OS (HC3-HC4).
 
2. Under high illumination and high chart luminance, record the distance (4 meter) ETDRS low contrast visual acuity twice OD (LC1-LC2) and twice OS (LC3-LC4).
 
3. With the goggles on, under normal illumination and chart luminance, record the distance (4 meter) ETDRS high contrast visual acuity twice OD (HC5-HC6 and twice OS (HC7-HC8). Allow subject to adjust to dim condition for 3 minutes.
 
 
Letter-by-letter results will be recorded into the electronic data capture form, which will calculate the visual performance score for each chart read.
	[REDACTED]
1.24	Subject Reported Ocular Symptoms	Subjects will respond to a verbal open-ended symptoms questionnaire.	[REDACTED]
1.25	CLUE Post-Fit Questionnaire	The subject will respond to the CLUE Post-Fit Questionnaire	[REDACTED] Appendix A
1.26	Cosmetic Lens Fit Assessment (without slit-lamp)	The Cosmetic Lens Assessment will be assessed by the investigator (without slit-lamp) in primary gaze and extreme gaze (right, left, and upgaze) at a normal conversation distance (approximately three (3) feet away from the subject).	Appendix D
1.27	Hula Hoop Assessment (without slit-lamp) *If unacceptable cosmetic fit in any gaze.*	If there is an unacceptable cosmetic fit in any gaze, the Hula Hoop Assessment will be assessed by the investigator (without slit-lamp) in primary gaze and extreme gaze (right, left, and upgaze) at a normal conversation distance (approximately three (3) feet away from the subject).	Appendix D

# Clinical Study Protocol

## Johnson & Johnson Vision Care, Inc.

1.28	Subjective Lens Fit Assessment	
Evaluate overall lens fit acceptance (acceptable or unacceptable) based on centration, movement and other fitting characteristics.
 
An unacceptable fit is deemed by one of the following criteria:
 
 
• Presence of limbal exposure (appearance of clear cornea) in any gaze;
 
• Presence of edge lift;
 
• Presence of unacceptable movement (excessive or insufficient) in all three of the following conditions: primary gaze, up gaze, and tightness on push up.
 
 
Note: if lens fit is unacceptable subject will be discontinued from the study.
	
1.29	Wettability Characteristics	Record the white light lens wettability of both lenses.	
1.30	Surface Deposits	Record any front and back surface lens deposits.	
1.31	Continuance	
For the subject to continue in the study, they must meet all three of the following criteria:
 
 
• Visual acuity is 20/30 or better OD and OS
 
• The lens fit is acceptable OD and OS
 
• Investigator approval. If the Investigator does not approve the dispensing of the first study lens, then the study is terminated for that subject.
 
	
1.32	Dispense	
The lenses will be dispensed for a 5 to 7 day wearing period. During this time, they are required to wear the lenses at least 6 hours per day.
 
 
• Dispense enough lenses to last the subject to their scheduled follow-up visit. Do not dispense extras*.
 
• The lenses will be worn as daily wear/daily disposable only.
 
• Rewetting drops are permitted if needed.
 
	

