### 2.3. Hypotheses

#### Primary Hypothesis

1. The proportion of eyes with corrected distance monocular visual acuity 0.176 logMAR or better (ie, Snellen VA 20/30 or better) using the Test lenses under high illumination/high contrast is superior to 90%.

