## 8. SUBJECTS COMPLETION/WITHDRAWAL

### 8.1. Completion Criteria

Subjects are considered to have completed the study if they:

- provided informed consent and/or assent;
- they are eligible;
- Completed all study visits;
  - Have not withdrawn/discontinued from the study for any reason described in Section 8.2

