### 8.2. Withdrawal/Discontinuation from the Study

A subject will be withdrawn from the study for any of the following reasons:

- Subject death during the study period
- Subject withdrawal of consent and/or assent
- Subject not compliant to protocol
- Subject lost to follow-up
- Subject no longer meets eligibility criteria (eg the subject becomes pregnant)
- Subject develops significant or serious adverse events causing discontinuation of study lens wear
- Subjects who have experienced a Corneal Infiltrative Event (CIE)
- Investigator's clinical judgment regarding the subject safety reasons (that it is in the best interest of the subject to stop treatment)

For discontinued subjects, the Investigator will:

- Complete the current visit (scheduled or unscheduled)
- Complete the Final Evaluation, indicating the reason that the subject was discontinued from the study
- Record the spherocylindrical refraction with best corrected distance visual acuity, as appropriate.

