##### **Per-Protocol Population:**

All subjects who have successfully completed all visits and did not substantially deviate from the protocol as determined by the trial cohort review committee prior to database hard lock (Per-Protocol Population). Justification of excluding subjects with protocol deviations in the Per-Protocol Population set will be documented in a memo to file.

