### 14.5. Primary Analysis

#### Visual Acuity (logMAR)

Distance monocular high luminance high contrast visual acuity data will be dichotomized into two groups where  $Y=1$  if subjects VA is below 0.176 logMAR and  $Y=0$  otherwise;  $Y$  will be analyzed using a generalized linear mixed model with the logit as the link function. Sequence of lens wear, study period and lens type will be included in the model as fixed effects. Other characteristics such as age may be included as covariates in the model. Site will be included as a random effect (G-side). The covariance between residual errors from the same subject and eye across study periods will be modeled using either homogenous compound symmetry (CS) or unstructured (UN). The structure that returns the lowest finite-sample corrected Akaike's Information criterion will be selected as the structure that best fits the model. The Kenward and Roger method, will be used for the denominator degrees of freedom. The proportion of eye with 0.176 logMAR or better while wearing the Test lens will be estimated using a 95% confidence interval for the estimated proportion.

The null and alternative hypothesis to test for superiority of the Test relative to the pre-defined threshold 0.176 logMAR is as follows:

$$H_o: P_{Test} \leq 90\%$$
$$H_A: P_{Test} > 90\%$$

Superiority will be declared if the lower limit of the 95% confidence for the estimated proportion of eyes with distance monocular high luminance high contrast VA better than 0.176 logMAR while wearing the Test lens is above 90%. i.e.  $P(p_{Test} > 90\%) \geq 0.975$ .

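### Does leaving the primary analysis population unnamed let the 20/30 continuance step remove Test-lens failures from the primary test?

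*Combined protocol and SAP*

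**What the plan says.** The primary hypothesis (Section 2.3) concerns the proportion of eyes at "0.176 logMAR or better (ie, Snellen VA 20/30 or better) using the Test lenses", to be shown superior to 90%. Section 14.5 gives the model and the decision rule: "The proportion of eye with 0.176 logMAR or better while wearing the Test lens will be estimated" with a 95% confidence interval, and the lower limit must exceed 90%. It does not say in which population.

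Section 14.3 defines three sets: Safety, Per-Protocol and Intent-to-Treat. Per-Protocol is "All subjects who have successfully completed all visits and did not substantially deviate from the protocol". Section 8.1 likewise lists "Completed all study visits" among its conditions for completion. The ITT set keeps every randomised subject with at least one observation, including those who withdraw.

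The order of events at a fitting visit matters:

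- **Steps 1.22 and 3.10 (Snellen):** "Record the distance Snellen visual acuity (OD, OS, and OU) to the nearest letter with the study contact lens correction in place".
- **Steps 1.23 and 3.11 (ETDRS, the endpoint):** "record the distance (4 meter) ETDRS high contrast visual acuity twice OD (HC1-HC2) and twice OS (HC3-HC4").
- **Steps 1.31 and 3.19 (continuance):** "Visual acuity is 20/30 or better OD and OS", together with an acceptable fit and investigator approval. Neither step says which acuity reading applies.

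For a subject who is discontinued, Section 8.2 tells the investigator to "Complete the current visit (scheduled or unscheduled").

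**The concern.** The continuance step screens subjects at the endpoint's own threshold, on the same lens and at the same visit. A subject who fails it on the Test lens cannot complete all visits, so she leaves the Per-Protocol set and takes her failing eye or eyes with her. If that set carried the primary test, failures would be removed from a test of whether failures are rarer than 10%. The estimate would be too high, and the 2.5% error rate in the direction of success could be exceeded.

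Because Section 14.5 is silent, a later choice of Per-Protocol would not count as a departure from the plan under Section 14.10. Section 14.2 also speaks of about 40 completers, which can be read as the intended analysis size.

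**Working it through.** **1. The plan's own figure.** Section 14.2 gives 34 subjects for a Test proportion of 0.995 against 0.90, eye correlation 0.627 and two-sided 5%. The effective number of eyes is 2 × 34 / 1.627 = 41.8, about 42. An exact test at one-sided 2.5% on 42 eyes rejects only if all pass (0.90^42 = 0.012), and its power is 0.995^42 = 0.81. So 34 meets 80% power by the exact test. A normal approximation with null variance would ask for 38. Nothing below depends on which is used.

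**2. How many subjects have a failing Test eye.** P(both eyes pass) = p² + 0.627·p(1 − p).

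- p = 0.90: 0.81 + 0.627 × 0.09 = 0.866. Then 13.4% of subjects have at least one failing eye, or 6.7 of 50.
- p = 0.995: 0.9931. Then 0.69% have one, or 0.34 of 50.

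**3. What a Per-Protocol test would show.** Let c be the share of subjects with a failing Test eye whom continuance removes. With P(exactly one eye fails) = 2p(1 − p)(1 − 0.627) = 0.0671 at p = 0.90, the retained proportion is [0.866 + (1 − c)·0.0671/2] / [0.866 + (1 − c)·0.134]. False success is simulated, using an exact 95% lower limit on effective eyes.

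| c | Retained proportion, true 0.90 | False success, N = 40 | False success, N = 50 |
|---|---|---|---|
| 0 (all kept) | 90.0% | 1.3% | 1.3% |
| 0.50 | 94.6% | 10.6% | 14.6% |
| 0.75 | 97.2% | 29% | 39.6% |
| 0.90 | 98.9% | 60% | 71% |

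**4. What share is removed.** The documents do not give it. If continuance used the ETDRS reading, every failing Test eye would go. If it used Snellen, the share depends on agreement between the two readings. The next table simulates the Test fitting alone, with 50 subjects, true proportion 0.90 and latent eye correlation 0.884 (which reproduces 0.627). The assumed latent Snellen–ETDRS correlation is 0.6, 0.8 or 0.95.

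| Snellen assumption | Failing eyes removed | False success |
|---|---|---|
| Error independent between eyes, same cut-off | 59 / 74 / 88% | 13 / 31 / 67% |
| Error shared between eyes, same cut-off | 45 / 63 / 83% | 6 / 19 / 55% |
| Independent, Snellen cut-off 0.5 SD more lenient | 32 / 43 / 49% | 5 / 9 / 13% |
| Shared, 0.5 SD more lenient | 24 / 34 / 45% | 4 / 7 / 11% |
| All fitted Test eyes kept | 0% | about 1.2% |

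The retained proportion runs from 92% to 99%. The bias is always upward, but its size rests on assumptions that the documents cannot settle. The decision rule here is also not the mixed model of Section 14.5.

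**5. Which set the plan points to.**

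- Section 14.1 says results for each subject or eye are used whenever they exist.
- The ITT definition keeps withdrawn subjects.
- Section 14.9 plans a multiple-imputation sensitivity analysis if dropout exceeds 15%. That has no purpose in a completers-only analysis.
- The 40 completers in Section 14.2 are introduced as an allowance for dropout, not as an analysis set.
- No section gives Per-Protocol any role in the primary test.

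The data support this reading. Steps 1.23 and 3.11 come before 1.31 and 3.19, so a subject stopped on the Test lens already has her endpoint reading.

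**The case for a change.** The strongest reply is that a confirmatory test should name its population. The leanings in Sections 14.1 and 14.9 are not an assignment, and one sentence would close the question. Descriptive efficacy results also go to the responsible clinician and project lead after 20 completers (Section 14.8), while the choice is formally open. Error control matters for a lens near 90%, not only at the planning value, and there the inflation under Per-Protocol could be large.

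The omission is real, and so is the direction of the bias. It also stands that steps 1.31 and 3.19 leave the acuity reading unnamed. Snellen is the natural one, since the criterion is written in Snellen notation and steps 1.22 and 3.10 are headed simply as visual acuity. What does not stand is that the plan leads to the biased analysis: that takes a choice for which the text gives no support.

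A second point is that keeping all fitted Test eyes does not recover Control-first subjects who are stopped on Control and never wear Test. With Control at 0.995, false success for all fitted eyes stays at 1.2–1.6%. With Control at 0.90, an assumed value, 3.3–4.4 of 25 Control-first subjects would be lost and false success would be 1.8–7.5%. That loss is a limit of the crossover with a continuance step. Naming a population would not remove it.

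**Conclusion.** No change follows. Section 14.5 omits a detail, and the rest of the plan supplies a sensible answer: analyse every eye with a Test-lens ETDRS reading at fitting, whether or not the subject continued. On that set, false success at a true 90% is about 1.2–1.3% under the approximation used here, apart from any loss of Control-first subjects on Control.

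The harm arises only if Per-Protocol or completers were made primary. Then 24–88% of failing Test eyes would be removed under the assumed Snellen–ETDRS agreement (all of them if the ETDRS reading governed), and false success would be 3.5–67%. Those ranges rest on undocumented correlations, cut-offs and error structures. At the planning value of 0.995, which Section 14.2 takes from earlier data on the same Test lens, about 0.34 of 50 subjects would have a failing Test eye. Even removing all of them would move the estimate only from 99.5% to 100%.

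A reader of the study report should check that subjects stopped on the Test lens are counted in the primary result.

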## Clinical Study Protocol

### Johnson & Johnson Vision Care, Inc.

		
 
• A patient instruction booklet will be provided.
 
• Subjects will be scheduled for their 5-7-day follow-up visit, ensuring that they wear the study lens at least 6 hours on the day of the follow-up visit.
 
 
* Note: In the event a lens is lost or damaged, the subject will return to the clinical site for replacement. As much as reasonably possible, a damaged lens and packaging should be returned to the clinical site (wet, if possible) and then returned to the Sponsor. If lens damage is present, complete the Product Quality Complaint Form. The lens will be stored in labeled vial with saline, and clearly differentiated from the other worn lenses that will be shipped back to the Sponsor.
	
--	--	---	--

#### VISIT 2

The subjects must present to Visit 2 wearing test article for at least six (6) hours on the day of the visit.

Visit 2: Treatment 1 Follow-Up			
Step	Procedure	Details	[REDACTED]
2.1.	Adverse Events and Concomitant Medications Review	Review the subject's concomitant medications and record any changes from the previous study visit. Record any adverse events or medical history changes from the previous study visit.	[REDACTED]
2.2.	Wearing Time	Record the average wearing time and comfortable wearing time.	[REDACTED]
2.3.	Compliance	Confirm compliance with the prescribed wear schedule.	[REDACTED]
2.4.	Subject Reported Ocular Symptoms	Subjects will respond to a verbal open-ended symptoms questionnaire.	[REDACTED]
2.5.	CLUE Follow-Up Questionnaire	The subject will respond to the CLUE Follow-Up Questionnaire	[REDACTED]
2.6.	Entrance Visual Acuity	Record the distance Snellen visual acuity (OD, OS, and OU) to the nearest letter with study contact lens in place. Subjects must	[REDACTED]

# Clinical Study Protocol

## Johnson & Johnson Vision Care, Inc.

		read the smallest line until at least 50% of the letters are read incorrectly.	
2.7.	Cosmetic Lens Fit Assessment (without slit-lamp)	The Cosmetic Lens Assessment will be assessed by the investigator (without slit-lamp) in primary gaze and extreme gaze (right, left, and upgaze) at a normal conversation distance (approximately three (3) feet away from the subject).	Appendix D
2.8.	Hula Hoop Assessment (without slit-lamp) *If unacceptable cosmetic fit in any gaze.*	If there is an unacceptable cosmetic fit in any gaze, the Hula Hoop Assessment will be assessed by the investigator (without slit-lamp) in primary gaze and extreme gaze (right, left, and upgaze) at a normal conversation distance (approximately three (3) feet away from the subject).	Appendix D
2.9.	Subjective Lens Fit Assessment	
Evaluate overall lens fit acceptance (acceptable or unacceptable) based on centration, movement and other fitting characteristics.
 
An unacceptable fit is deemed by one of the following criteria:
 
 
• Presence of limbal exposure (appearance of clear cornea) in any gaze;
 
• Presence of edge lift;
 
• Presence of unacceptable movement (excessive or insufficient) in all three of the following conditions: primary gaze, up gaze, and tightness on push up.
 
 
Note: if lens fit is unacceptable subject will be discontinued from the study.
	
2.10	Wettability Characteristics	Record the white light lens wettability of both lenses.	
2.11	Surface Deposits	Record any front and back surface lens deposits.	
2.12	Remove lenses	The lenses will be removed and discarded.	
2.13	Slit Lamp Findings	FDA Slit Lamp Classification Scale will be used to grade the findings. Adverse events shall be documented and followed for significant slit lamp findings.	

## Clinical Study Protocol

### Johnson & Johnson Vision Care, Inc.

		If the clearance of the fluorescein needs to be expedited, preservative-free rewetting drops may be instilled.	
2.14	Washout instructions	Subjects are instructed to wear their spectacles or habitual contact lenses for 2-5 days.	
2.15	Exit Visual Acuity	Record the distance Snellen visual acuity (OD, OS, and OU) to the nearest letter with their habitual spectacles (where applicable). Subjects must read the smallest line until at least 50% of the letters are read incorrectly.	

### VISIT 3

The subjects must present to Visit 3 not wearing their habitual contact lenses.

Visit 3: Treatment 2 Treatment			
Step	Procedure	Details	[REDACTED]
3.1.	Adverse Events and Concomitant Medications Review	Review the subject's concomitant medications and record any changes from the previous study visit. Record any adverse events or medical history changes from the previous study visit.	
3.2.	Visual Acuity	Record the distance Snellen visual acuity (OD, OS, and OU) to the nearest letter with the habitual spectacle correction (if needed) in place. Subjects must read the smallest line until at least 50% of the letters are read incorrectly.	
3.3.	Slit Lamp Findings	FDA Slit Lamp Classification Scale will be used to grade the findings. Adverse events shall be documented and followed for significant slit lamp findings. If the clearance of the fluorescein needs to be expedited, preservative-free rewetting drops may be instilled.	
3.4.	Continuance	Confirm the subject is able to continue in the study.	
3.5.	Lens Selection	Assign the study lens based on the randomization scheme. Select the contact lens power based on the vertexed (12 mm), spherical equivalent subjective refraction.	
3.6.	Lens Insertion	The Subject inserts the study lenses. Record the time of lens insertion.	

